2.1.4.2 Secondary efficacy endpoints

2.1.4.2.1 Crude ACPR at Day 28

Derived from the efficacy evaluation at Day 28 defined as follows:

Efficacy evaluation at Day 28	Per-Protocol Crude ACPR at Day 28	miITT Crude ACPR at Day 28
ACPR	Success	Success
ETF	Failure	Failure
LCF before Day 7	Failure	Failure
LCF on or after Day 7 or LPF		
- P. falciparum recrudescence	Failure	Failure
- P. falciparum reinfection prior to Day 28	Failure	Failure
- P. falciparum reinfection on Day 28	Failure	Failure
- Other species mixed with P. falciparum recrudescence	Failure	Failure
- Other species mixed with P. falciparum reinfection	Failure	Failure
- Undetermined, negative or missing PCR	Failure	Failure
Other species infection without P. falciparum reemergence	Excluded from analysis	Failure
Rescue therapy start without previous ETF, LCF, LPF, or other species infections, and not classified as a protocol violation	Failure	Failure
Lost to follow-up	Excluded from analysis	Failure
Withdrawal*	Excluded from analysis	Failure
Protocol violation**	Excluded from analysis	Failure

(*): Patient's request - Investigator's judgement - Adverse event - Other

(**): protocol violations potentially impacting efficacy assessment at Day 28 for the PP population are defined in [Section 2.3.2.2](#)

2.1.4.2.2 Parasitemia at baseline then every 6 h during the first 36 h then at 48 h and every 24 h until Day 7

Parasitemia is the quantitative content of parasites in the blood. It is used as a measurement of parasite load in the organism and an indication of the degree of an active parasitic infection.

The methods to be used for quantifying parasitemia depend on the parasitic species and its life cycle. The number of plasmodia can be counted using an optical microscope, on a special thick film (for low parasitemias) or thin film blood smear (for high parasitemias).

2.1.4.2.3 Parasite clearance time (PCT)

For a conservative approach, parasite clearance should not be claimed based on negative parasitemia obtained by imputation. Therefore, in this section **no imputation of missing parasitemia** will be used, except in case of concomitant fever where the missing parasitemia will be considered as positive.

Timing to consider

In this section, except otherwise specified, the post-dose timing associated to a parasitemia will refer to:

- its assigned time point as defined in [Section 2.5.4.1](#), if it exists,
- its actual post-dose timing as defined in [Section 2.5.4](#) and expressed in hours, if outside defined time windows. None or very few are expected, otherwise it should be taken into account in the analyses.

Establishing the clearance

A blood thick film is considered negative when asexual forms of *P. falciparum* are reported as absent on the dedicated e-CRF page, even if other species are reported.

The parasite clearance will be concluded as soon as two consecutive thick films are negative, with second film prepared within 6 to 12 hours of the first (actual times). In case, the second film has been performed less than 6 hours or greater than 12 hours of the first, then the parasite clearance will be confirmed or invalidated by the thick film following the second one, whatever the timing of this third film:

- If this third film is negative, then the clearance is confirmed.
- If this third film is positive, then the clearance is invalidated.

Time to parasite clearance

When the parasite clearance is confirmed, the time to parasite clearance is the post-dose timing associated to the first negative thick film, as defined above.

In case the parasite clearance is not observed or confirmed before withdrawn (for any reason) or before start of rescue therapy, then the time to parasite clearance will be censored at the time of the last blood film (using the post-dose timing above defined) before withdrawn or rescue therapy start, whichever comes first. Blood films (including date and time of recording) performed the day of rescue start are regarded as before rescue.

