6.2 EXCLUSION CRITERIA

Participants are excluded from the study if any of the following criteria apply:

Medical conditions

- E 01. Presence of severe malaria (6, 7)
- E 02. Known history or evidence of clinically significant gastrointestinal, cardiovascular, hepatic, renal, hematological, respiratory, endocrine, immunological, infectious, neurological (in particular convulsions), malignancy, psychiatric disease or symptoms which, in the judgment of the investigator, might confuse the interpretation of the safety information
- E 03. Severe vomiting defined as more than 3 times in the 24 hours prior to enrollment in the study or inability to tolerate oral treatment or severe diarrhea defined as 3 or more watery stools per day
- E 04. Severe malnutrition defined as a body mass index of less than 16 kg/m² (18) for adults and for children Z-score <-3 or weight for age (%) of the median <60
- E 05. Splenectomized participants or presence of surgical scar on left hypochondrium
- E 06. Known history of hypersensitivity, allergic, or anaphylactoid reactions to FQ or other amino quinolines or to OZ439 or OZ277 or any of the excipients

Prior/concomitant therapy

- E 07. Participant treated with anti-malarial treatment:
 - With PQP-based compound, mefloquine, naphthoquine or sulphadoxine/pyrimethamine within the previous 6 weeks.
 - With amodiaquine or chloroquine within the previous 4 weeks.
 - With quinine, halofantrine, lumefantrine-based compounds and any other anti-malarial treatment or antibiotics with antimalarial activity (including cotrimoxazole,

- tetracyclines, quinolones and fluoroquinolones, and azithromycin) within the past 14 days.
- With any herbal products or traditional medicines, within the past 7 days
- E 08. Previous treatment within 5 times the half-life or within the last 14 days, whichever the longest, which are: strong CYP2C or CYP3A inhibitors and/or moderate inhibitors but inhibiting both CYP2C and CYP3A and/or CYP inducers (Appendix 6)
- E 09. Any treatment known to induce a prolongation of QT interval (Appendix 6)

Prior/concurrent clinical study experience

- E 10. Participated in any trial investigating OZ439 and/or FQ compounds
- E 11. Previous participation in any malaria vaccine study or received malaria vaccine in any other circumstance
- E 12. Enrolled in another clinical trial within the past 4 weeks or during the study period

Diagnostic assessments

- E 13. Mixed *Plasmodium* infection

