7.7 CONCOMITANT THERAPY

All drugs other than oral contraceptives, paracetamol (acetaminophen) at the maximum dose of 40 mg/kg/day, metoclopramide if repeated vomiting and beta-lactams for any infection needing an antibiotic treatment are prohibited over the entire study period unless medically justified. The dosage and number of dose(s) will be recorded. The use of other contraceptive methods may be discussed. Traditional and herbal remedies are not permitted during the study.

Appendix 6 is listing drugs that can interfere with OZ439 or FQ metabolism (strong cytochrome P450 [CYP] 2C or CYP3A inhibitors, moderate inhibitors inhibiting both CYP2C and CYP3A, and CYP inducers) or can be affected by OZ439 and FQ in their metabolism (CYP2D6 main substrates, P-glycoprotein [P-gp] substrate) and drugs that can increase QT interval.

Any medication or vaccine (including over-the-counter or prescription medicines, vitamins, and/or herbal supplements) that the participant is receiving at the time of enrollment or receives during the study must be recorded along with:

- Reason for use
- Dates of administration including start and end dates
- Dosage information including dose and frequency

The Medical Monitor should be contacted if there are any questions regarding concomitant or prior therapy.

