In addition, except where otherwise specified, the following imputation rules will apply in case of missing or out of time window parasite count at a protocol scheduled time point, where the missing count occurs before rescue treatment start, before or on Day 28, or in absence of concomitant fever. In such cases, the missing parasitemia will be considered as:

- positive, if followed or preceded by positive parasitemia,
- negative, if preceded and followed by negative parasitemia,
- missing, if no parasite count available thereafter.

In above bullets:

- positive parasitemia means *P. falciparum* parasite count from thick film ≥ 1 parasite/ μ L, otherwise the parasitemia is negative.
- parasite count from thick film performed after rescue treatment start cannot be used for imputation of missing or out of time window parasite count.

- parasite count from thick film performed the day of rescue treatment start can be used for imputation because this is regarded as before rescue treatment.

In case of concomitant fever related to malaria event (fever is defined in [Section 2.1.4.2.8](#)), a missing parasitemia will be always considered as positive.

In case of missing (or out of time window) parasite count at successive protocol scheduled time points, the above imputations rules could be extended after endorsement of the imputations by the clinical team, otherwise the case will be classified as a deviation preventing evaluation of ACPR as listed in [Section 2.3.2.2](#). Cases of missing body temperature concomitantly with positive parasitemia (observed, or put in place of a missing parasite count as explained above) will be imputed, according to the same principle as for parasitemia imputations, after endorsement of the imputations by the clinical team, or will be classified as deviation.

Efficacy evaluation

Efficacy evaluation will use Early Treatment Failure (ETF), Late Clinical Failure (LCF), Late Parasitological Failure (LPF), and Adequate Clinical and Parasitological Response (ACPR) definitions given below.

Table 1 - Revised WHO classification of treatment failures in areas of intense malaria transmission

Criterion
ETF is defined as one of the following :

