2.3.2 Efficacy populations

2.3.2.1 *Modified Intent-to-treat population*

The modified intent-to-treat (mITT) population includes all randomized patients who received the single administration of IMP, with parasitologically confirmed *P. falciparum* malaria at baseline, having parasitemia data post-randomization.

For analyses and displays, patients will be classified according to the randomized treatment regardless of actual treatment received.

2.3.2.2 *Per-protocol population*

The per-protocol (PP) is the population receiving at least the single administration of FQ 400mg/OZ439, with parasitologically confirmed malaria at baseline, having parasitemia data post-randomization in order to be evaluable for Day 28 ACPR, without major protocol violations possibly affecting efficacy outcome. Note PCR-corrected ACPR applies only to recrudescence i.e. patients with new infections are considered non-evaluable for the analysis of PCR-corrected ACPR see Section 2.1.4).

Parasitemia data for patients with rescue treatment started before the considered time point will be excluded from this time point until Day 28.

In case of vomiting or other reasons interrupting the administration of the complete dose, and if valid parasitemia data post-randomization available, then patients will be included in the PP population.

As defined in [Section 2.1.4.1](#), there are certain criteria that would exclude patients from having an evaluable PCR-corrected ACPR at Day 28:

- Other species infection without *P. falciparum* reemergence,
- Lost to follow-up,
- Withdrawal,
- Protocol violation.

Protocol violations considered above are those potentially impacting efficacy assessments at Day 28:

- Patients who did not take IMP or who needed rescue treatment due to vomiting during IMP administration. Start of vomiting will be classified in 3 categories (< 5 minutes, [5-35] minutes, > 35 minutes and < 6 hours).
- Patient presenting severe malaria or receiving a rescue treatment due to severe malaria during the first 24 hours following IMP start (i.e. wrong inclusion).
- Start of rescue therapy before Day 28 assessment not due to: vomiting during IMP administration, wrong inclusion, treatment failure (per investigator or per WHO criteria), or other species infections.
- Missing baseline parasitemia, and positive parasitemia at 48 or 72 hours.
- Intermittent missing or out of window post-baseline parasitemia preventing to evaluate ACPR Day 28.

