2.4.4.2.2 Parasitemia

Descriptive statistics (n, mean, geometric mean, standard deviation, median, Q1, Q3, minimum, and maximum) for parasitemia data (number of parasites/ μ L) (raw data and absolute change from baseline) will be displayed at baseline, and each post-baseline assessment.

Time profile plots (Mean \pm SEM) of parasitemia will be provided for each treatment arm, one curve per arm.

Box-Whisker plots over time of positive parasitemia levels will be provided by treatment arm.

Assessments performed after start of rescue treatment will not be included in above summaries

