2.4.4.2.4 Parasite clearance rate and derived parameters

The parasite clearance rate, PC50, PC99 and estimated parasite reduction ratios (PRR24, PRR48 PRR72) will be summarized descriptively. However, data from patients with a poor fit to the linear model ($R^2 < 0.75$) will be excluded from the analysis.

2.4.4.2.5 Parasite clearance half-life (time to 50% parasite reduction) and time to 99% parasite reduction

Point estimate and 95% confidence interval for the geometric mean of T_{PC50} and T_{PC99} will be provided pooled across the 4 treatment group and separately for each dose group, using a linear fixed effect model.

Descriptive statistics (such as median, minimum, and maximum) will be provided for each treatment arm.

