2.5 DATA HANDLING CONVENTIONS

2.5.1 General conventions

The following formulas will be used for computation of parameters.

Demographic formulas

- Body mass index (kg/m^2) = (Weight in kg)/ (Height in meters)²
- Time from first diagnosis of current malaria infection: day of randomization - day of diagnosis of current malaria infection
- Prior/concomitant/follow-up medications:

Only the date of medication start/end will be reported in the eCRF (no time), then by convention medication taken the day of randomization will be classified as concomitant.

Renal function formulas

Creatinine clearance value is derived using the equation of Cockroft and Gault: CrCl is calculated using weight assessed at the same visit than creatinine was assessed.

For patients > 18 years old:

$CrCl (mL/min) = F \times (140 - \text{age(years)}) \times \text{weight(kg)} / [\text{serum creatinine } (\mu\text{mol/L})]$ where F = 1.23 if male, and 1.04 if female

For patients ≤ 18 years old (Bedside Schwartz Formula):

$eGFR (\text{mL/min}/1.73 \text{ m}^2) = (0.413 \times \text{Height in cm}) / [\text{serum creatinine } (\mu\text{mol/L})]$

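### On mITT, parasite reduction ratio and clearance-rate endpoints have no rescue cut-off, so decline caused by rescue drugs before 72 h would count as study-arm effect

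*SAP*

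**What the plan says.** **Where a rescue cut-off exists.** For the parasitemia summaries, SAP 2.4.4.2.2 states: "Assessments performed after start of rescue treatment will not be included in above summaries". The PP definition (SAP 2.3.2.2) states: "Parasitemia data for patients with rescue treatment started before the considered time point will be excluded from this time point until Day 28". The PK/PD efficacy definition (2.3.5.1) repeats that rule. Time to parasite clearance (2.1.4.2.3) is censored at the last film before rescue.

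**Where none is written.** Observed PRR (2.1.4.2.9, 2.4.4.2.3), clearance rate (2.1.4.2.10, 2.4.4.2.4), T50 and T99 (2.1.4.2.11, 2.4.4.2.5) and estimated PRR (2.1.4.2.12) carry no rescue condition. For the fitted quantities the SAP says only that the rate, PC50, PC99 and "estimated parasite reduction ratios (PRR24, PRR48 PRR72) will be summarized descriptively", after dropping fits with R² below 0.75. SAP 2.4.4.2 puts all secondary efficacy endpoints except crude ACPR on mITT alone, and the mITT definition has no rescue exclusion. The Summary of statistical analyses table at the end of SAP Appendix B lists PP for the same endpoints.

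**Same-day films.** For clearance time, "Blood films (including date and time of recording) performed the day of rescue start are regarded as before rescue". For imputation, "parasite count from thick film performed the day of rescue treatment start can be used for imputation because this is regarded as before rescue treatment". On medication times, SAP 2.5.1 says: "Only the date of medication start/end will be reported in the eCRF (no time").

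**Other antimalarial drugs after dosing.** Protocol E 07 names "antibiotics with antimalarial activity (including cotrimoxazole", tetracyclines, quinolones and azithromycin, among others). Under Protocol 7.7, drugs outside a short permitted list "are prohibited over the entire study period unless medically justified". The violation lists in SAP 2.3.2.2 and 2.3.5.1 cover E 07 drugs only before dosing.

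**The concern.** Protocol 7.7.1 keeps blood films going to Day 28 after rescue, so post-rescue counts will be in the database. A programmer who follows the SAP body text would use them for PRR and for the clearance slope. A patient rescued early because the study treatment was vomited or was failing could then score like a full responder. SAP 2.1.4.2.9 sets a zero count to 1/µL, so any patient with a negative film at 72 h gets a PRR72 equal to the baseline count, whichever drug cleared the parasites.

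The same-day convention adds to this: with dates only, a film taken hours after rescue cannot be told from one taken before it. The antibiotic gap is separate and touches ACPR, because a drug with antimalarial activity taken for another indication is neither rescue nor a listed violation.

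**Working it through.** The plan gives no figure on this point. Its constants check: ln 2 = 0.693 and ln 100 = 4.605, so T99 = 4.605/k.

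**1. Rules side by side**

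| Endpoint | Population | Counts after rescue |
|---|---|---|
| Parasitemia summaries | mITT (body) | dropped |
| Time to parasite clearance | mITT (body) | censored; rescue-day films kept |
| Observed PRR | mITT (body), PP (table) | no rule on mITT; dropped on PP |
| Clearance rate, T50, T99, estimated PRR | mITT (body), PP (table) | no rule on mITT; dropped on PP |

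Whether the cut-off applies therefore depends on a population that the SAP states in two ways.

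**2. Effect of the missing cut-off.** Assumptions, none from the documents: baseline 10,000/µL, own clearance k1 = 0.02 to 0.08 per h, clearance after rescue k2 = 0.15 to 0.25 per h, detection at about 8/µL. Undetectable counts are set to 1/µL, as the SAP does.

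Rescue at 24 h:
- Own decline: PRR72 = exp(72·k1), which is exp(1.44) = 4.2 to exp(5.76) = 317.
- No cut-off, slowest case: the log fall is 0.02·24 + 0.15·48 = 7.68, so the count is 10,000·exp(−7.68) = 4.6/µL. That is undetectable and becomes 1/µL, so PRR72 = 10,000. All nine combinations of three k1 and three k2 values give 10,000.
- Slope of log count on the scheduled detectable films: 0.082 to 0.137 per h, so T99 is 34 to 56 h against 58 to 230 h from own decline. R² is 0.81 to 0.97, so the 0.75 filter removes none of the nine. This is an ordinary log-linear fit, not the WWARN estimator.

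Rescue at 48 h:
- PRR24 and PRR48 are unaffected. PRR72 is 96 to 10,000 against 4.2 to 317.
- Of the nine slopes, five are unchanged because the 72 h film is undetectable and leaves the fit, two fall below R² 0.75 and are removed, and two stay in and are distorted (0.054 against 0.02; 0.077 against 0.05).

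Rescue at hour 0: PRR24 = exp(24·k2) = 37 to 403, against exp(24·k1) = 1.6 to 6.8. This comes from the missing cut-off, not the same-day rule, since the 24 h film falls on the next date.

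**3. Effect on an arm.** Take 30 patients, 29 with PRR72 of 10,000 and one rescued at 24 h with k1 = 0.05 (own PRR72 = exp(3.6) = 36.6). The geometric mean is 10,000 without a cut-off. Counting that patient's own decline, it is 10,000·(36.6/10,000)^(1/30) = 8,294; with three such patients, 5,706. Excluding them also gives 10,000. Exclusion removes a wrong value but does not supply the right one, so the number removed must be shown.

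**4. Same-day leak into clearance time.** Time to an undetectable count is ln(P/8)/k2:

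| Count at rescue (/µL) | k2 = 0.15 | 0.20 | 0.25 |
|---|---|---|---|
| 20 | 6.1 h | 4.6 h | 3.7 h |
| 100 | 16.8 h | 12.6 h | 10.1 h |
| 3,000 | 39.5 h | 29.6 h | 23.7 h |

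At enrolment densities (3,000/µL or more), a false clearance later on the rescue day is unlikely. At 20 to 100/µL it is possible, most easily for the endpoint in SAP 2.4.4.2.6 that needs no confirming film.

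**5. Antibiotic gap.** SAP Table 1 denies ACPR for a failure criterion or earlier rescue. SAP 2.1.7 defines a Day 0 to Day 28 window for other antimalarials but attaches no outcome rule. A medically justified course of an E 07 antibiotic after dosing therefore leaves a patient eligible to be a success.

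**The case against.** **The SAP does have a cut-off.** It does for PP and PK/PD efficacy, and following the summary table would apply it to PRR and clearance rate. A reader might infer that the SAP has no rescue rule at all; that is not so. What stands is the mITT analysis in the body text and its conflict with the table.

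**Few patients can be affected.** Two of the four early-failure criteria use the Day 3 film itself, so that film precedes rescue and PRR72 is clean. Contamination needs rescue for vomiting, danger signs, a Day 2 count above Day 0, or an investigator decision. Patients who vomit before OZ439 may not meet the mITT dosing requirement. All of this limits the number; none of it supplies a rule.

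**The same-day convention has a reason.** Protocol 7.7.1 asks for a film before rescue where possible, and with dates only, dropping every rescue-day film would lose the one that established failure. This stands, and it is why the remedy is a recorded time rather than a blanket exclusion. The absence of a rescue time is inferred from a general medication convention; the e-CRF is not among the documents.

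**Dilution of the OZ439 contrast.** A reader might expect rescue mostly with FQ alone and conclude that the dose contrast shrinks. Failure rescue may well be commoner there, but rescue for vomiting after an OZ439 re-dose occurs only in the three OZ439 arms. The direction is not established.

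**Antibiotics.** Beta-lactams are the only antibiotics on the permitted list, other antimalarials are tabulated, and PP has a general clause on major violations. Use may be rare, and a medically justified course need not be a deviation.

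**Conclusion.** The concern holds for observed PRR, clearance rate, T50, T99 and estimated PRR on mITT. As written, the SAP body would credit post-rescue decline to the study arm in patients rescued before 72 h. For a single patient the error can be large: under the assumed rates with rescue at 24 h, PRR72 is 10,000 instead of 4 to 317, and T99 is 34 to 56 h instead of 58 to 230 h. For an arm, it depends on how many are rescued early, which the documents do not give.

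The same-day rule is a lesser leak, limited to later films on the rescue date and mainly to low residual counts.

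A reader might infer that rescue inflates the primary endpoint. It does not, because ACPR requires no previous rescue. Sample size and power are untouched, and the SAP body plans no hypothesis test for PRR, clearance rate, T50 or T99. The one route to ACPR is post-dose use of other drugs with antimalarial activity. Such patients are possible failures; nothing in the documents shows that they are likely ones.

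**What to change.** 1. Reconcile SAP 2.4.4.2 (mITT only) with the summary table (PP) for these endpoints.
2. State in 2.4.4.2.3 to 2.4.4.2.5 that counts after rescue start are excluded for observed PRR, clearance rate, T50, T99 and estimated PRR, on mITT as well. Report by arm and time point how many values are removed for rescue.
3. Record the rescue start time. Failing that, use the clock time of the pre-rescue PK sample (Protocol 7.7.1 and 9.5) or of the pre-rescue film.
4. Add a sensitivity analysis that drops rescue-day films not documented as taken before rescue.
5. Add to the violation lists in SAP 2.3.2.2 and 2.3.5.1 the use, between dosing and the Day 28 film, of E 07 drugs with antimalarial activity other than as rescue for failure. Under the table in 2.1.4.1 a listed violation is excluded on PP and a failure on mITT, so confirm that this is intended.

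Cost: one e-CRF field, if time is not already captured, and a few sentences in the SAP. A few PRR values become missing, some slopes rest on fewer films, and a few patients may become non-evaluable for ACPR.
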